### Secondary endpoints

2. • *Parasite prevalence by microscopy at the end of the transmission season in all age groups [end-of-study survey].*

This endpoint will compare the parasite prevalence in all age groups between intervention arms.

3. *Parasite prevalence by qPCR at the end of the transmission season in all age groups (between arm comparison). [end-of-study survey].*

This outcome will be compared between arms as described above for outcome 1.

4. *Parasite prevalence by qPCR at the end of the transmission season compared between arms 1 and combined arms 2 + 3. [end-of-study survey].*

This outcome will be compared between arms as described above for outcome 1.

5. *Parasite prevalence by microscopy prior to SMC rounds 2, 3 and 4 in SMC-targeted age groups (between arm comparison). [at SMC-delivery].*

This outcome will be compared between arms as described above for outcome 1.

6. *Rate of re-infection with *P. falciparum* at weeks 3, 4 and 5 after the last round of SMC, assessed in SMC-targeted age groups (between arm comparison). [mid-study surveys].*

This outcome will be presented as prevalence estimates with 95% confidence intervals for each time-point. It will be compared between arms as described above for outcome 1.

7. *Gametocyte prevalence by qRT-PCR at weeks 3, 4 and 5 after the last round of SMC, assessed in SMC-targeted age groups (between arm comparison). [mid-study surveys].*

This outcome will be presented as prevalence estimates with 95% confidence intervals for each time-point and study arm separately. It will be compared between arms as described above for outcome 1.

8. *Gametocyte prevalence by qRT-PCR at the end of the transmission season in all age groups (between arm comparison). [end-of-study survey].*

This outcome will be presented as prevalence estimate with 95% confidence interval for each study arm separately. It will be compared between arms as described above for outcome 1.

9. *Gametocyte prevalence by qRT-PCR at the end of the transmission season in age groups targeted by SMC (comparison between arm1 and 2 (in children aged 3-59 months) and arms 2 and arm 3 (in children aged 5 years-9 years). [end-of-study survey].*

This outcome will be presented as prevalence estimates with 95% confidence intervals for each time-point and study arm separately. It will be compared between arms as described above for outcome 1.

10. *Plasma levels of AQ and desethylamodiaquine (DEAQ) after the 4th round of SMC in children aged 3 months-9 years (between arm comparison) [post-SMC round 4].*

A published non-linear mixed-effects pharmacokinetic model will be evaluated for the ability to describe AQ and DEAQ pharmacokinetics in the study population (viii). All quantifiable plasma concentrations available will be used for model evaluation using gold-standard methods. Visual predictive checks and goodness-of-fit plots will be made to assess model performance for participants in which dosing history is observed through DOT. For each study participant 2000 full concentration-time profiles will be simulated, considering participant age and weight, assuming full treatment adherence.

Model-predicted concentrations at the PK sampling time will be determined for each simulation. The optimal cut-off percentile discriminating between adherence and non-adherence was previously determined to be the 20th percentile of the individual simulated concentration-time profiles (71% sensitivity, 80% sensitivity) (viii). Participants with observed plasma concentrations below the individual cut-off percentile will be scored as non-adherent. Coverage will be expressed as percentage of participants scored as non-adherent per treatment arm. Additional analyses will include the percentage of participants with/without any measurable AQ or DEAQ plasma concentrations.

*11. Incidence of clinical malaria captured during passive-case detection (between arm comparison) [[post-SMC round 4]]*

Passive case detection data will be analysed by Poisson regression. The outcome will be the number of cases in each compound. Comparisons will be made between arms 1 and 2 in children aged 3-59 months and between arms 2 and 3 in children aged 5-9 years. There will be a random effect for compound and an offset of the number of children.

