### 2.3 Design & intervention

The study is designed to evaluate SMC effectiveness and consists of three interventional study arms, with the first arm receiving an intervention that is implemented as part of routine control.

Study arm 1:	SMC in children under the age of 5 years, implemented by the Ministry of Health (MoH) without directly observed treatment for the full course of SMC
Study arm 2:	SMC in children under the age of 5 years, with directly observed treatment for the full course of SMC
Study arm 3:	SMC in children under the age of 10 years, with directly observed treatment for the full course of SMC

SMC consists of SP and AQ administered daily for three days. SP is given on the first SMC day only while AQ is given daily over three days. In total 4 rounds of SMC will be conducted during the peak malaria transmission season from July to October, separated by approx. 30 days.

Each study arm contains 62 clusters; each cluster consists of 3 compounds where each compound has at least one child aged 3-59 months and one child aged 5-9 years. (186 compounds per arm; 558 compounds in total). Differences in SMC coverage and efficacy will be determined in the SMC-targeted age groups. In contrast, all age groups will take part in the evaluation of the study to assess the impact of the intervention on the infectious reservoir in the community and compare parasite carriage in targeted and untargeted populations. To detect possible behavioural contamination and differences in SMC uptake or adherence in study arm 1 compared to what would be observed if there would be no

study team present, a single cross-sectional survey 7 days after the last (4th) round of SMC coverage is assessed outside the study area (2-5 kilometres from the nearest enrolled study compound) by questionnaire and samples to determine plasma levels of SMC drugs and parasite carriage by qPCR. Plasma levels of SMCR drugs are used as the most definitive evidence of differences in SMC uptake/adherence.

Scheduled surveys and scheduled or unscheduled sampling timepoints will take place in each arm; these surveys are designed and timed for several outcome measures and include:

- i) a survey prior to first SMC roll-out (performed in all compounds).
- ii) mid-study surveys 3, 4 and 5 weeks after the last SMC roll out (each compound will participate in one of these surveys).
- iii) end-of-study survey up to 10 weeks after last SMC roll out (performed in all compounds).

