### Primary endpoint

1. *Parasite prevalence by quantitative PCR (qPCR) at the end of the transmission season in age groups targeted by seasonal malaria chemoprevention. [end-of-study survey].*

This endpoint will be compared between arms 1 and 2 (in children aged 3-59 months) and arms 2 and arm 3 (in children aged 5 years--9 years). Parasite prevalence by qPCR will be used as binary variable with all parasite densities above 100 parasites/mL (0.1 parasite/ $\mu$ L) being classified as parasite positive. Parasite prevalence is compared between arms by logistic regression; models will account for clustering by including cluster as a random intercept and village as a fixed effect.

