single modelled association will be used. If drug levels do have a statistically significant impact on transmission potential, all estimates of the infectious reservoir within one month of SMC will take study arm into account. For the infectious reservoir at the final end of study survey, no impact of SMC drugs on transmission efficiency is assumed. The contribution of different age groups (younger than 5 years, 5–15 years, 16 years and older) to the infectious reservoir will be estimated using all data (including parasite-negative observations where zero transmission is assumed)

14. *Prevalence of drug resistance markers in infected children aged 3 months-9 years assessed post each round of SMC (between arm comparison) [during the entire study].*
15. *Description of perceived social barriers to SMC uptake [during the entire study].*
16. *Quantification of SMC efficacy decay under programmatic conditions [during the entire study].*

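### The all-age comparisons do not separate SMC-targeted from untargeted ages, and endpoint 13's 5–15 year band straddles the arm 3 treatment limit at 10 years

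*SAP*

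**What the plan says.** Section 2.3 (Design & intervention) gives two reasons for surveying every age group: to assess the effect on the community's infectious reservoir, and to "compare parasite carriage in targeted and untargeted populations". Objective iii in section 4 asks how much different age groups contribute to transmission under conventional SMC (under 5 years) and extended SMC (under 10 years).

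Section 10.7 then sets out the analyses:

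- Outcome 1 covers targeted ages only. "This endpoint will be compared between arms 1 and 2 (in children aged 3-59 months"), and between arms 2 and 3 in those aged 5–9 years. The model is a logistic regression, and "models will account for clustering by including cluster as a random intercept and village as a fixed effect". It has no age term.
- Endpoint 2 (microscopy) says "This endpoint will compare the parasite prevalence in all age groups between intervention arms". It names no model.
- Endpoint 3 is "Parasite prevalence by qPCR at the end of the transmission season in all age groups (between arm comparison"), and endpoint 8 is its gametocyte counterpart. Both refer back to outcome 1; for endpoint 3 the text is "This outcome will be compared between arms as described above for outcome 1".
- Endpoint 13 (infectious reservoir) is the only all-age analysis with bands: "younger than 5 years, 5–15 years, 16 years and older".

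**The concern.** The SAP states an aim, the comparison of targeted with untargeted people, and supplies no analysis for it. Endpoints 2, 3 and 8 are its natural home, but they do not say whether all age groups means one pooled comparison or one per group, and they define no groups. The cross-reference to outcome 1 does not help, because the ages named there are the targeted ones.

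Arm 3 differs from arm 2 only in treating 5–9 year olds. A pooled contrast between them therefore contains the direct effect in those children plus any indirect effect in everyone else, and cannot show how much is which. The banding in endpoint 13 has a related fault. Its middle band crosses the age at which treatment stops in arm 3, so the newly targeted ages cannot be read off under extended SMC, which is what objective iii needs. If the split at 10 years is chosen after the data are seen, it becomes a post hoc choice.

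**Working it through.** **Which bands are mixed.** Setting the arms in section 2.3 against the bands in endpoint 13, with 5–15 split at the arm 3 limit:

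| Age | Arm 1 | Arm 2 | Arm 3 |
|---|---|---|---|
| Under 5 | SMC, programme | SMC, observed | SMC, observed |
| 5–9 | none | none | SMC, observed |
| 10–15 | none | none | none |
| 16 and over | none | none | none |

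The 5–15 band is homogeneous in arms 1 and 2 and mixed in arm 3. The 16+ band is untargeted in every arm. For arm 1 versus arm 2, both 5–15 and 16+ are untargeted.

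**Size of the pooled difference when the effect is purely direct.** The plan gives no figure for an all-age comparison, so there is none to reproduce. Inputs:

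- prevalence of 40% without and 25% with SMC (section 7, stated for ages 5–10 and taken here as 5–9);
- 1.5 children aged 5–9 per compound (section 6);
- compound size S, which the SAP does not give; assumed 8 to 12;
- no effect of arm 3 over arm 2 in any other age group.

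All other ages cancel between the arms, so the pooled difference is (1.5 / S) × (40 − 25) points:

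- S = 8: 0.1875 × 15 = 2.8 points
- S = 12: 0.125 × 15 = 1.9 points

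**How often that would be significant.** I used the standard formula for unmatched cluster trials, with c clusters per arm, m persons per cluster and coefficient of variation k:

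power = Φ( |p0 − p1| × √[(c − 1) / (p0(1 − p0)/m + p1(1 − p1)/m + k²(p0² + p1²))] − 1.96 )

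As a check against section 7's 87% (55 clusters, k = 0.3, 40% versus 25%), it gives 87.2% with 4 children per cluster and 95.4% with the 6 stated there. That mismatch is a separate matter, and the present point does not depend on it.

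For the pooled contrast I used 62 clusters, m = 3S, k = 0.3, 7% in under-5s in both arms (section 7, observed SMC) and an assumed 20% to 40% at age 10 and over.

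- S = 8, 20% at age 10 and over: arm 2 = (1.5 × 0.07 + 1.5 × 0.40 + 5 × 0.20) / 8 = 21.3%; arm 3 = (1.5 × 0.07 + 1.5 × 0.25 + 5 × 0.20) / 8 = 18.5%. Odds ratio 0.84; significant in about 34% of trials.
- S = 12, 40% at age 10 and over: 35.9% versus 34.0%. Odds ratio 0.92; significant in about 12% of trials.

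All combinations with S from 8 to 12 lie between these two. Restricted to age 10 and over under the same assumptions, the expected difference is zero and the rejection rate is the nominal 5%.

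**The case against.** Several counter-arguments are sound and limit the point.

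- **The pooled contrast is legitimate.** The rationale in section 2.2 concerns the whole infectious reservoir, and fewer infections in treated 5–9 year olds are a real part of that. Leaving out age does not bias a randomised comparison. The SAP nowhere calls endpoint 2, 3 or 8 an indirect effect. A reader might infer that a direct effect will be reported as community protection, but the document does not say so. The primary endpoint will also show the 5–9 year result alongside.
- **Untargeted estimates are not ruled out.** A reader might conclude that no reading of the plan yields one. That is not so. With endpoint 13's bands, 16+ is untargeted throughout and 5–15 is untargeted for arm 1 versus arm 2. Under-5s receive the same observed SMC in arms 2 and 3, so that band carries no direct difference between them either. The fault is confined to 5–15 in arm 3.
- **The bands belong to endpoint 13.** It is tempting to apply 5–15 to prevalence and quote 40% versus 32.5% (equal numbers and 40% in both halves, 0.5 × 25% + 0.5 × 40%). The SAP plans no prevalence comparison in that band, so the figure does not describe one of its analyses. Nor are these the only age groups in the plan: 3–59 months and 5–9 years appear in endpoints 1, 9 and 11, though for targeted children only.
- **A never-targeted contrast is not the community effect.** Clusters are three compounds randomised within villages, so neighbours may be in different arms. A null result at age 10 and over would not show that community benefit is absent.

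None of this supplies the comparison promised in section 2.3 or separates treated from untreated children within 5–15 in arm 3.

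**Conclusion.** The point stands in a limited form, for secondary and exploratory endpoints; the primary endpoint is correctly restricted by age. Section 10.7 has no analysis for a stated aim, and endpoint 13 uses a cut that does not match the treatment boundary objective iii depends on.

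On the plan's own 40% and 25%, and with compounds of 8 to 12 members, a purely direct effect leaves a pooled arm 3 versus arm 2 difference of 1.9 to 2.8 points. It would be significant in roughly 12% to 34% of trials, so confusing direct with indirect effects is possible rather than likely. Compound size, prevalence at age 10 and over, and the use of 0.3 as the all-age coefficient of variation are assumptions. That the pooled difference is not zero depends on none of them.

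**What to change.** - **Endpoint 13:** replace the bands with under 5, 5–9, 10–15 and 16 and over, using age at SMC round 1 as section 10.7 already requires.
- **Endpoints 2, 3 and 8:** state whether a pooled result is intended. Beside it, report the outcome 1 model separately in targeted and never-targeted ages: 10 years and over for arms 2 versus 3, and 5 years and over for arms 1 versus 2. Name this model for endpoint 2.
- **Labels:** call the pooled result an overall effect. Call the never-targeted contrast an indirect-effect estimate that may be diluted by spillover between neighbouring clusters.

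The cost is SAP wording and a few more model runs, with no new data because all ages are already surveyed. Intervals for the untargeted ages will be wider than for the pooled result.

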An exact sample size justification for the single cross-sectional survey in the area outside the study-targeted population is complicated; this survey is performed to give a broad indication of the potential influence the presence of our study team may have on the operational delivery of SMC in arm 1. It is not part of any main comparisons. Estimates of adherence are based on questionnaire data, supported by measurements of DEAQ drug levels in plasma. In arm 2 and 3 (Directly Observed Treatment (DOT); by design full adherence), the median level of DEAQ at day 4 following the last dose of AQ is expected to be 550 ng/mL (IQR 350-850). Based on a large assessment of reported adherence and measured AQ/DEAQ plasma levels following SMC in Niger (viii), we anticipate that <50% of children show complete adherence in arms 1 and the control village and >20% of the children in these populations may fail to take any dose. If we conservatively assume that

this results in a reduction of median DEAQ levels to <400ng/mL (IQR 200-700), we can estimate the power to detect this difference when enrolling 120 children in the SMC-targeted age range in the control area. For this, we assume that these DEAQ levels stem from right-skewed (log-normal) distributions; giving median log DEAQ concentrations of 6.31 (IQR 5.86-6.75) for DOT and 5.99 (IQR 5.30-6.55) for non-DOT. If it is further assumed that the distribution of the logged values is normally distributed, we can estimate the standard deviation through the IQR as  $IQR/1.349$ , giving standard deviations of 0.93 and 0.66, respectively. Using a sample size of 120 per group, and a Welch's two sample t-test for testing the differences between the log DEAQ concentrations, we estimate a power of 86.3% to detect these differences. Based on these assumptions, we are confident that sampling 120 children <5 years of age will allow meaningful assessments. As indicated above, this sample size estimation is not relevant for any of the main comparisons in the study but merely used to ensure informative sampling and avoid exposing an unnecessarily large population to the small discomfort of a single finger prick sample. We will thus aim to determine plasma levels of at least 120 children <5 years in arm 1; 120 children <5 years from arms 2 and 3 combined and 120 children from the control area.

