### 10.3 Effectiveness of SMC and SMC efficacy decay

*Assessing effectiveness of SMC requires collection of data on:*

- *Coverage (proportion of children reached by the four SMC rounds)*
- *Health Care worker's compliance (proportion of children receiving first dose of SMC under DOT)*
- *Caregiver's compliance (proportion of children receiving correct SMC regimen)*
- *Drug levels (proportion of children with adequate drug level)*

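### Endpoint 10 reports non-adherence under the name of coverage, using an uncorrected cut-off that flags about 20% of fully observed children and roughly halves the arm 1 versus DOT difference

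*SAP*

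**What the plan says.** Section 10.7, endpoint 10, concerns AQ and DEAQ plasma levels "after the 4th round of SMC in children aged 3 months-9 years (between arm comparison"). For each participant, 2000 profiles are simulated, "considering participant age and weight, assuming full treatment adherence". The cut-off is "the 20th percentile of the individual simulated concentration-time profiles (71% sensitivity, 80% sensitivity"). A child whose observed level lies below that child's own cut-off is scored non-adherent. The result is then reported as follows: "Coverage will be expressed as percentage of participants scored as non-adherent per treatment arm". An additional analysis gives the share with any measurable AQ or DEAQ.

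Other sections bear on this:

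- Section 10.3 opens with a list of separate quantities. The first is "Coverage (proportion of children reached by the four SMC rounds"); the share with an adequate drug level is a different item.
- Section 10.3, SMC treatment coverage, expresses coverage in arms 2 and 3 by the number of daily doses the target population received. It also says that adherence is evaluated from plasma levels in all participants.
- Section 2.3 says that coverage differences are determined in the age groups targeted by SMC. Arms 1 and 2 treat only children under 5 years.
- Section 7 describes the DOT arms thus: "In arm 2 and 3 (Directly Observed Treatment (DOT); by design full adherence"). Its minimum plasma samples in the study arms are from children under 5.

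**The concern.** There are three separate faults.

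1. **Label.** A percentage of non-adherent children is named coverage, so the reported figure rises as adherence falls. The same word already has two other meanings in section 10.3.
2. **Built-in false positives.** A 20th-percentile cut-off on a full-adherence distribution puts about one fully adherent child in five below it. No adjustment is planned, so arms that section 7 regards as fully adherent by design will show about 20% non-adherence, and the contrast with arm 1 will shrink.
3. **Denominator.** Neither endpoint 10 nor the adherence sentence in 10.3 limits scoring to children who were due SMC, although section 2.3 does so for coverage differences. Endpoints 5, 6, 7, 9 and 11 name targeted or arm-specific ages; endpoint 10 does not.

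Section 2.2 lists imperfect adherence and achieved drug concentrations as separate candidate explanations for SMC failure, and section 2.3 treats plasma levels as the most definitive evidence on uptake and adherence. A score that calls low levels in fully observed children non-adherence blurs those two explanations.

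**Working it through.** **Inputs.** Cut-off percentile 20%; accuracy 71% and 80% (10.7, endpoint 10). Fewer than 50% completely adherent expected in arm 1; full adherence in arms 2 and 3; median log DEAQ 6.31 (IQR 5.86–6.75) under DOT and 5.99 (IQR 5.30–6.55) without DOT; 120 children per group (section 7). On average 1.5 children under 5 and 1.5 aged 5–9 per compound (section 6).

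**The plan's own power figure.** SD = IQR width / 1.349 gives 0.89/1.349 = 0.66 for DOT and 1.25/1.349 = 0.93 for non-DOT. The text prints them in the opposite order, with no effect on power. Standard error = √[(0.66² + 0.93²)/120] = 0.104; difference = 0.32. A Welch test at two-sided 0.05 (assumed) has 86.4% power, against 86.3% stated. The figure reproduces.

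**What the 80% is.** One cut-off cannot have two sensitivities. If the model is calibrated, the share of adherent children above their 20th percentile is 1 − 0.20 = 0.80, which is specificity. A simulation with 2000 draws per child put 19.5% of fully adherent children below the cut-off.

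**Effect in targeted children.** With true non-adherence p, the scored share is 0.71p + 0.20(1 − p) = 0.20 + 0.51p. The DOT arms (p = 0) score 20%.

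| True non-adherence, arm 1 | Scored, arm 1 | Raw difference from DOT | True difference |
|---|---|---|---|
| 20% | 30.2% | 10.2 points | 20 points |
| 30% | 35.3% | 15.3 points | 30 points |
| 50% | 45.5% | 25.5 points | 50 points |
| 70% | 55.7% | 35.7 points | 70 points |

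The factor is 0.71 + 0.80 − 1 = 0.51. If sensitivity here were 10 points lower or higher (my assumption), it would be 0.41 or 0.61.

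**Check against section 7's distributions.** The DOT 20th percentile is 6.31 − 0.842 × 0.66 = 5.75 on the log scale, about 316 ng/mL. The non-DOT share below it is about 40%, so the raw contrast is 40% versus 20%.

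**Power of the raw binary contrast** (120 per group, clustering ignored): 99% for 45.5% versus 20%, 76% for 35.3% versus 20%, and 44% for 30.2% versus 20%.

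**If untreated children were scored** (section 2.3 set aside). With ages 50:50 and every untreated child below the cut-off (assumption), a fully adherent arm 2 would score 0.5 × 20% + 0.5 × 100% = 60%, and arm 3 would score 20%. With 40–60% under-5s and 95–100% of untreated children below the cut-off, arm 2 ranges from 0.6 × 20% + 0.4 × 95% = 50% to 0.4 × 20% + 0.6 × 100% = 68%.

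**The case against.** **Age pooling.** A reader might infer that arm 2 will look far worse than arm 3, at 60% against 20%. The documents do not support this as a forecast. Section 2.3 places coverage differences in targeted ages, section 7 plans its minimum samples in under-5s, and 10.3 times sampling from when the last dose was due, which presupposes a treated child. The age span in endpoint 10 may simply be the union of the ages targeted across arms. What stands is that endpoint 10 and 10.3, read literally, conflict with 2.3 and must be reconciled.

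**Other measures.** The score is not the only use of the drug data. Section 7 sizes a comparison of continuous log DEAQ, and endpoint 10 adds the share with any measurable drug; the cut-off affects neither. This limits the damage but does not repair the measure that endpoint 10 reports.

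**Transparency.** The plan states the accuracy of the cut-off, the DOT arms will show the background rate, and model fit is checked in participants with observed dosing. These help interpretation, but none changes the reported contrast.

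**Uncertain inputs.** The 20% needs a calibrated model. The 71% comes from another population and depends on the mix of partial and missed courses; section 7 expects more than 20% to take no dose, and they are easier to detect than partial takers. This stands, so a range is needed.

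**Limits of a correction.** Taking the false-positive rate from DOT children forces their estimated non-adherence to 0% and could hide poor absorption, which objective iv (section 4) covers. This also stands: the corrected figure belongs beside the raw one, not in its place.

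**Conclusion.** The point holds for endpoint 10 as written. The reported quantity is the inverse of its name. If the model is calibrated, about 20% of fully observed children are scored non-adherent. At 71% and 80% accuracy the raw arm 1 versus DOT difference is about half the true one: 25.5 instead of 50 points at 50% true non-adherence, and 10 to 36 instead of 20 to 70 points over the range 20–70%. These sizes rest on complete adherence in the DOT arms and on the 71% carrying over to this population.

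A reader might infer that the contrast could change sign, or that the prevalence results are in doubt. Neither follows. A false-positive rate shared by the arms pulls the difference towards zero without reversing it. The endpoint is secondary, the primary endpoint does not use the score, and power stays high if arm 1 adherence is as poor as section 7 expects. The 50–68% against 20% for arm 2 versus arm 3 applies only if section 2.3 is ignored.

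**What to change.** 1. In 10.7, endpoint 10, and in 10.3, restrict adherence scoring to children targeted by SMC in their arm, consistent with 2.3. Compare arm 1 with arms 2 and 3 in ages 3–59 months.
2. Report the percentage adherent (100% minus the share scored non-adherent), call it adherence, and keep coverage for doses received.
3. Report the raw share below the cut-off for each arm. Beside it give a corrected arm 1 versus DOT contrast, (raw arm 1 − f)/(Se − f), with a cluster-bootstrap interval. Here f is the share below the cut-off among children with all doses observed, and Se runs over a range around 71%. For example, raw values of 45.5% and 20% give 0.255/0.51 = 50 points at Se 0.71, 0.255/0.41 = 62 at Se 0.61, and 0.255/0.61 = 42 at Se 0.81.
4. State that low levels in fully observed children are read as exposure or absorption, not as non-adherence.
5. Check the cited source and change the second sensitivity to specificity.

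The cost is a few lines of SAP text and a short calculation on data already planned. The corrected contrast will have a wider interval than the raw one.

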- iv) sampling for drug metabolite assessment shortly after the last SMC round (sample collection in all compounds in the study arms and outside-study control area).
- v) sampling for transmission assay on first day of SMC round 2 to 4 (sampling in all compounds; selection from individuals aged 5-9 years).
- vi) passive case detection in all four health facilities that are accessed by the study population throughout the study period (from enrolment until the end of follow-up).

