### **3 Randomization**

The unit of randomization will be the cluster; each cluster comprises of 3 compounds. Clusters are randomly allocated to one of the three study arms by a computer generated algorithm and stratified by village. Stratification by village was to account for spatial differences in malaria exposure, distance from health facilities, and treatment seeking behavior. In total, 185 clusters were randomized.

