## 7 Sample size considerations

Evaluable study clusters will comprise 3 compounds and have between 4-5 children below 5 years of age (eligible for standard SMC) and similar numbers of children aged 5-10 years (eligible for SMC in study arm 3). We assume ~40% parasite prevalence detected by PCR at the end of the transmission season in children aged 5-10 without SMC and 16% parasite prevalence in children aged <5 years under programmatic SMC (based on recently completed work in the same area Collins, Ouedraogo et al. in prep). When assuming a reduction to 25% parasite prevalence in children aged 5-10 years when included in SMC, a sample size of 55 clusters per arm (x3 compounds per cluster and an estimated total 6 children in this age group per cluster) will achieve 87% power to detect this difference at an alpha of 0.05 and a coefficient of variation of 0.3 (data from INDIE 1a; LSHTM EC #14724; Centre National de Recherche et de Formation sur le Paludisme institutional review board (Deliberation N° 2018/000002/MS/SG/CNRFP/CIB; Burkina Faso national medical ethics committee (Deliberation N° 2018-01-010)). This sample size will also allow the detection of a reduction of parasite prevalence in directly observed SMC to 7% as

compared to 16% under programmatic SMC, in children under 5 years of age. The total number of compounds per arm has been increased to 62 to mitigate the effects of non-compliance and drop-outs and also for logistical reasons, such whole villages are included. We will thus enrol a total of 186 clusters over 3 arms in a ratio of 1:1:1 with 558 compounds in total. We anticipate that this will include a minimum of 720 children below 5 years of age (2 per compound, based on recent census data) and 720 children aged 5-9 years (1 per compound as per inclusion criterion).

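### The clinical-malaria model (endpoint 11) has a random effect for compound only, so it misses the correlation between compounds of the same randomised cluster

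*SAP*

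**What the plan says.** SAP section 3 defines the design: "The unit of randomization will be the cluster; each cluster comprises of 3 compounds". Allocation was stratified by village, to account for spatial differences in malaria exposure, distance from health facilities and treatment seeking.

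Section 10.7 carries this design into the primary analysis: "models will account for clustering by including cluster as a random intercept and village as a fixed effect". Endpoints 3 to 9 adopt that model by referring to outcome 1.

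Endpoint 11, clinical malaria found by passive case detection, has its own model: "Passive case detection data will be analysed by Poisson regression. The outcome will be the number of cases in each compound". Arms 1 and 2 are compared in children aged 3-59 months, and arms 2 and 3 in children aged 5-9 years. The specification ends: "There will be a random effect for compound and an offset of the number of children". It does not refer to outcome 1 and names neither cluster nor village. No other section adds these terms.

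**The concern.** Each comparison uses one age group, so each compound contributes one row. A random effect with one row per unit can only model extra-Poisson variation. It cannot link the three compounds of a cluster, which the model then treats as independent although they were allocated together. If they are positively correlated beyond what village explains, the standard error of the arm contrast is too small.

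This is the only clinical-disease outcome among the endpoints in section 5, so readers will give it weight. The reasons given for stratifying by village, such as distance from health facilities and treatment seeking, plausibly bear directly on passively detected cases.

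Two pieces of wording in the same entry also leave room for misreading: the offset, and the tag that places the endpoint after SMC round 4.

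**Working it through.** The SAP states no power, rate or error figure for endpoint 11, so there is nothing to reproduce. The check asks how far the compound-only standard error departs from the correct one.

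**Inputs from the SAP**
- 3 compounds per cluster and 62 clusters per arm (section 2.3). The variance ratio below does not depend on the number of clusters.
- 1.5 children per compound in each age group (section 6).
- The sample size in section 7 is set "at an alpha of 0.05 and a coefficient of variation of 0.3". That CV is given for parasite prevalence; using it for incidence is an assumption.

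**Assumptions**
- Rate r of 0.1 to 1 case per child, so mean cases per compound m = 1.5r.
- Cluster CV k of 0.3 or 0.5, and compound CV c of 0 or 0.3.
- Two-sided alpha of 0.05.

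**Formula.** Let f be the share of cluster variance that lies between villages. Stratified allocation largely removes that share from the arm contrast, but a model without village still counts it as error.

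- Modelled variance per compound: m + m²(c² + k²)
- True variance per compound: m + m²c² + 3m²(1 − f)k²
- V = true / modelled
- Type I error = 2[1 − Φ(1.96/√V)]

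**Step 1: all cluster variation within villages (f = 0), c = 0**

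| Cases per child | V, k = 0.3 | Type I error | V, k = 0.5 | Type I error |
|---|---|---|---|---|
| 0.1 | 1.03 | 5.3% | 1.07 | 5.8% |
| 0.3 | 1.08 | 5.9% | 1.20 | 7.4% |
| 0.5 | 1.13 | 6.5% | 1.32 | 8.8% |
| 1.0 | 1.24 | 7.8% | 1.55 | 11.5% |

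At 1 case per child with c = 0.3 and k = 0.3, V = (1.5 + 0.2025 + 0.6075)/(1.5 + 0.405) = 1.21, so type I error is 7.5%. With k = 0.5, V = (1.5 + 0.2025 + 1.6875)/(1.5 + 0.765) = 1.50, giving 10.9%. The modelled standard error is about 1 to 10% too small at k = 0.3, and up to about 20% too small at k = 0.5.

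**Step 2: simulation under no arm difference** (1000 trials per scenario, 62 clusters per arm, no village effect, log of children as offset)

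| Cases per child | k | c | Compound effect only | Cluster-robust |
|---|---|---|---|---|
| 0.3 | 0 | 0.3 | 5.1% | 5.6% |
| 0.3 | 0.3 | 0.3 | 6.1% | 5.7% |
| 1.0 | 0 | 0.3 | 4.0% | 4.3% |
| 1.0 | 0.3 | 0.3 | 8.6% | 5.5% |
| 1.0 | 0.5 | 0.3 | 9.9% | 4.2% |

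Monte Carlo error is about 0.7 points. Without between-cluster variation the planned model is valid; with it, the error rises, and taking variance at cluster level brings it back to about 5%.

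**Step 3: part of the variation between villages** (1 case per child, c = 0.3)

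| f | V, k = 0.3 | Type I error | V, k = 0.5 | Type I error |
|---|---|---|---|---|
| 0 | 1.21 | 7.5% | 1.50 | 10.9% |
| 1/2 | 1.05 | 5.6% | 1.12 | 6.5% |
| 2/3 | 1.00 | 5.0% | 1.00 | 5.0% |
| 1 | 0.89 | 3.8% | 0.75 | 2.4% |

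V equals 1 exactly when 3(1 − f) = 1, that is f = 2/3, whatever the rate or CV. A simulation with village-stratified allocation (1500 runs, 31 villages assumed) shows the same pattern for f = 0, 1/2 and 2/3: 8.7%, 6.8% and 5.3% at k = 0.3, and 11.1%, 7.3% and 5.9% at k = 0.5.

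**The case against.** The strongest reply is that the effect is small and its direction uncertain. The rates and the CV of 0.5 have no source in the SAP, and the CV of 0.3 belongs to prevalence. At 0.1 case per child and CV 0.3 the error is only 5.3%. Because allocation was stratified, leaving village out inflates the modelled error and offsets part or all of the shortfall. The endpoint is secondary, and the SAP gives no power calculation for it. All of this stands and limits the size of the point. It does not rescue the model: the two omissions balance at one particular variance split, which nobody can know in advance, and away from it the intervals are too narrow or too wide.

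Three stronger readings are tempting, and the document does not support them.

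- *The standard errors ignore between-cluster variation altogether.* They do not. The compound effect absorbs that variance into the total; only the correlation among compounds of one cluster is lost.
- *The offset is wrong because it is a raw count.* The phrase is most naturally shorthand for the denominator of a rate. The SAP nowhere says that it enters unlogged, and Stata, one of the named packages, can take a count as exposure and log it. Nor does the SAP indicate follow-up differences that would make child-time essential.
- *The post-round-4 tag discards the peak-season cases.* Section 2.3 says that passive detection runs "throughout the study period (from enrolment until the end of follow-up", which describes data collection. An endpoint may use only part of what is collected, and the tag stands in both endpoint lists, so it may be deliberate. What is missing is a plain statement of which cases count.

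**Conclusion.** The point holds for the level of the random effect and the missing village term. As specified, the endpoint 11 standard errors are not valid for a design that randomises clusters of three compounds within villages. If cluster variation lies mainly within villages they are too small, with type I error of about 5 to 8% at cluster CV 0.3 and up to about 11% at CV 0.5. If more than about two-thirds of it lies between villages they are too large. These figures rest on assumed rates of 0.1 to 1 case per child and on assumed CVs, since the SAP gives neither for incidence.

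This should be fixed before analysis. It does not threaten the trial's main conclusion: the primary endpoint, and the secondary endpoints that borrow its model, already include cluster and village. The offset and the tag are matters of wording only.

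**What to change.** Replace the model sentence for endpoint 11 with: Poisson regression of the number of cases per compound, with a random intercept for cluster, a compound-level random effect for overdispersion, and village as a fixed effect, as for endpoint 1.

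In the same edit, make two clarifications. State that the offset is the log of the number of children (or of child-time). State the period over which cases are counted, so that the post-round-4 tag and the description of passive detection from enrolment to the end of follow-up agree.

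The cost is a few lines of SAP text and one model specification. Cluster and village are already recorded for the randomisation and used in the primary model, so no new data are needed. Intervals may become slightly wider.
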